8.12 Study Assessments

8.12.1 Demographics, Medical History and Medications

To the extent possible given the patient's medical condition, a medical history including family history of pancreatitis and smoking history will be collected at Screening. Demographic data will be collected and will include self-reported race, ethnicity and gender. Patients must be specifically questioned if they have had previous episodes of AP and if they have chronic pancreatitis, diabetes mellitus, hypertension, coronary or cerebrovascular disease, and chronic obstructive pulmonary disease, as well as those conditions noted in the exclusion criteria. The extent of alcohol consumption will be collected. Selected medications that were being taken prior to coming to the emergency department will be collected as will, if available, a baseline serum creatinine.

8.12.2 Concomitant Medications

The name, dose and frequency of selected medications that were administered will be recorded. The time, dose, and route of administration of opioid pain medications that are actually administered will be recorded. Generic names should be used when possible.

8.12.3 Abdominal Examination

An abdominal examination will be performed and recorded at Screening to assess if the patient has abdominal guarding or rebound tenderness. For eligibility purposes, an abdominal examination completed as SOC within 12 hours of consent or following consent but prior to randomization may be used for Inclusion Criterion 3b. Guarding is the voluntary contraction or involuntary spasm of the abdominal wall musculature to avoid pain from palpation of the abdomen and/or protect underlying inflamed viscera. Rebound tenderness is the elicitation of tenderness by rapidly and smoothly removing the examining hand. In addition, the presence or absence of the following symptoms should also be recorded at screening: bruising in the subcutaneous fatty tissue around the umbilicus and bruising in the flanks.

8.12.4 Vital Signs

The patient's temperature, heart rate (beats per minute), systolic and diastolic blood pressures and respiratory rate (breaths per minute) closest to the time of assessment should be recorded. If intra-abdominal pressures are being monitored, the pressure closest to the time of assessment should be recorded.

8.12.5 Arterial Blood Gas

If an arterial blood gas (ABG) has been performed as supportive care, the time of the draw and following results will be recorded: the pH, PaO₂, PaCO₂, SaO₂ and FiO₂.

8.12.6 SpO_2/FiO_2

The SpO₂ will be determined using a hospital approved pulse oximeter. The PI or appropriately trained delegate should review the pulse oximetry waveform determining the SpO₂ to attest to its adequacy. The FiO₂ at the time of the SpO₂ measurement will be recorded. For patients with assisted breathing, the FiO₂ is read from the controlled oxygen source e.g., Venturi masks, ventilator and CPAP/BIPAP systems with calibrated oxygen blenders. For patients breathing unassisted i.e., room air, the FiO₂ is recorded as 0.21. If a patient is on an uncontrolled oxygen source, the following table provides the estimated FiO₂:

Table 5. Conversion of O₂ Flow to FiO₂

Supplemental Oxygen L/min	Estimated FiO ₂ (%)			
	Nasal Cannula	Face Mask	Face Mask with Reservoir	
Room Air	21			
1	24			
2	28			
3	32			
4	36			
5	40	40		
6	44	50	60	
7		50	70	
8		60	80	
9		60	90	
10		60	95	

Adapted from Vincent 2009

8.12.7 Laboratory Analyses

At Screening, a lipase, CBC, differential, and platelets, will be performed at the local lab. For eligibility purposes, the results of the CBC collected within 24 hours of consent or following consent but prior to randomization will be used to determine the presence of SIRS (see Section 8.12.13) and a Hematocrit collected as SOC within 12 hours of consent or following consent but prior to randomization may be used for Inclusion Criterion 3c.

CBC with Differential and Platelets will be performed at 24, 48 and 72 hours, and if the patient remains hospitalized, at 120, 168, and 216 hours following SFISD as well as at Day 30 assessment. These samples will be sent to the local laboratory for analysis.

Serum Chemistries and Serum Procalcitonin will be performed at Baseline, 24, 48 and 72 hours, and if the patient remains hospitalized, at 120, 168, and 216 hours following SFISD as well as at Day 30 assessment. These samples will be sent to the local laboratory for analysis.

CBC results that should be reported in the eCRFs include absolute or percent neutrophil and lymphocyte counts. Serum chemistries reported in CRFs should include sodium, potassium, chloride, bicarbonate, blood urea nitrogen, creatinine, glucose, calcium, phosphorus, as well as magnesium, total protein, albumin, alkaline phosphatase, alanine transaminase (ALT), aspartate transaminase (AST), total bilirubin, lactate dehydrogenase (LDH), total cholesterol, triglycerides, and creatine kinase (CPK).

If a site is unable to perform any of the laboratory tests because it is not offered at the site, it will not be performed on patients randomized at the site.

Blood and urine samples for biomarker assessments (non-genetic testing) including, but not limited, to blood samples for IL-6 and urine samples for urine NGAL will be collected at baseline, 24, 48, and 72 hours, and if the patient remains hospitalized, at 120, 168, 216 hours following SFISD as well as at Day 30 assessment. A reference laboratory will analyze these blood and urine samples. The results of these assays will not be available to the PI or treating physician in managing the patient. It is the expectation that all sites participate in biomarker collection; however, if a site is unable to provide blood or urine samples for the biomarker analysis, this will be determined at study start and not considered a protocol deviation for that site. In addition, if a site is participating in biomarker collection but a patient does not want to provide biomarker samples this will be documented in the informed consent and not considered a protocol deviation.

8.12.8 PK analysis

Blood samples for PK analysis will be drawn as soon as possible after the completion of the first infusion of study drug (within +2 hours), prior to the start of second infusion of study drug (within -30 min), and at 72 hours (±2 hours) from the SFISD. If the patient is discharged after the third infusion of study drug and prior to 72 hours from the SFISD, the blood sample will be drawn prior to discharge. A PK sample will also be drawn at Day 30. The date and time that the sample for PK analysis is drawn shall be recorded. All samples for PK analysis should be stored at either -20°C or -80°C until shipment on dry ice to the central laboratory. As with the biomarkers, it is the expectation that all sites participate in the PK sample collection; however, if a site is unable to provide blood for the PK analysis, this will be determined at study start and not considered a protocol deviation for that site. In addition, if a site is participating in PK collection but a patient does not want to provide PK samples this will be documented in the informed consent and not considered a protocol deviation.

8.12.9 Enhanced Recovery Strategy for Tolerance of Solid Food

Patients randomized into the study will be offered a low fat, ≥500-calorie solid meal at each mealtime after the infusion of the first dose of study drug until discharge if alert and not on mechanical ventilation, or if not NPO for a planned surgery/medical procedure, or if not NPO because of an acute medical condition. See Section 5.2 for specific assessment procedures.

8.12.10 Modified ANMS GCSI-Daily Diary (mGCSI-DD)

The ANMS GCSI Daily Diary was designed to assess gastrointestinal symptoms associated with idiopathic and diabetic gastroparesis. It has been shown to be a reliable tool to evaluate dysmotility in patients with AP (Ma 2016). It will be used to assess gastrointestinal symptoms associated with AP in an exploratory manner. The mGCSI-DD has a 24-hour recall; thus, all items are designed to be self-administered on a daily basis.

The patient training for completing the daily diary is provided by the PI or appropriately trained delegate. Patients should understand their disorder: AP, where there is an abnormally delayed emptying of food from the stomach because of inflammation in the pancreas. The mGCSI-DD recording sheet and instructions are reviewed with the patient prior to the patient starting the recording of daily symptoms in the diary. The symptom severity response items are reviewed: "For each symptom listed below, please mark with an X the box that best describes the worst severity of each symptom during the past 24 hours. The next question asks you to record the number of times vomiting occurred in the last 24 hours. Please record the number of vomits (throwing up with food or liquid coming out) that occurred in the last 24 hours. Record zero, if you have not vomited during the past 24 hours. If you vomited, write down the number of all vomits. If you vomited once, record one. If you vomited three times during the day, record three. If you vomited three times, whether it was during the same trip to the bathroom or three separate trips, record three as the number of episodes of vomiting."

Patients discharged before Day 25 will complete the daily diary on the day of discharge, and then after discharge, daily at bedtime until the Day 30 visit.

8.12.11 Pain Numeric Rating Scale (PNRS)

In patients who are able to self-report their pain, the Pain Numeric Rating Scale (Appendix 4) will be used to grade the severity of the abdominal pain. It should be recorded if an opioid analgesic had been given in the 2 hours prior to the PNRS determination.

8.12.12 Contrast-Enhanced Computed Tomography (CECT) of the Abdomen/Pancreas

The recommended CECT protocol will consist of:

- A non-ionic contrast bolus of 100-150cc will be administered at 3-5cc/second
- Slice thicknesses will be 5 mm or less and will be obtained through the pancreas during the pancreatic phase (35 seconds after the start of the non-ionic contrast bolus) and through the entire abdomen during the portal venous phase (50 to 70 seconds after the start of the non-ionic contrast bolus) to visualize the pancreas and surrounding tissue

If CECT is not available (e.g. medical contraindication to contrast medium used in CECT) and another appropriate imaging is available (e.g. MRI, MRCP), please contact medical monitor to discuss whether local SOC imaging can be used for eligibility and Day 30 purposes.

CECT contrast protocol may be altered to local SOC. The lack of perfusion of the pancreas on the CECT will be exclusionary. If a CECT had already been performed more than 24 hours but less than 48 hours before Consent, and there is a contraindication to repeating it, the PI should discuss with the medical monitor if the CECT may be used for evaluating the inclusion and exclusion criteria for the study.

The PI or treating physician may also elect to delay the Day 30 CECT (± 5 days) due to patient-specific safety considerations but must inform the Medical Monitor of the decision. The PI or treating physician may also elect not to perform the CECT because of futility considerations, e.g., the patient is unlikely to survive in the next 48 hours but must discuss the decision with the Medical Monitor.

The CECT may also be used to make the diagnosis of chronic pancreatitis. Patients with a diagnosis of chronic pancreatitis in the chart or who self-report chronic pancreatitis but are neither on enzyme replacement nor following up with a gastroenterologist as an outpatient, should be considered for the study after a careful review of a CECT (Appendix 7). If the findings in the mild-moderate or severe categories are not present on the CECT, please contact the medical monitor to discuss whether the patient would be appropriate for randomization if they meet the other inclusion and none of the exclusion criteria. The 'equivocal' criteria do not exclude patients from randomization.

The Screening and Day 30 CECTs will be read by a blinded central reader. They will also be read locally and may be used by the PI or treating physician, as needed, for patient management.

If the patient undergoes additional CECTs at the discretion of the PI or treating physician from randomization to the Day 30 visit, the date of the CECT will be recorded and a blinded central reader will read the images.

8.12.13 Systemic Inflammatory Response Syndrome (SIRS)

The physician, or appropriately trained designee will determine the presence of SIRS at Screening. The most extreme value for each criterion in the 24 hours before consent may be used. SIRS is defined as the presence of at least 2 of the 4 criteria:

- Temperature $< 36^{\circ}$ C or $> 38^{\circ}$ C
- Heart rate > 90 beats/minute
- Respiratory rate > 20 breaths/minute or arterial carbon dioxide tension (PaCO2)
 32 mmHg
- White blood cell count (WBC) >12,000 mm3, or < 4,000 mm3, or > 10% immature (band) forms

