At 72 hours or Discharge (if earlier), 7 of 14 (50%) of patients receiving Auxora+SC (all doses) were able to tolerate solid food, defined as eating \geq 50% of a solid meal without vomiting or an increase in pain, compared to 1 of 7 (14%) patients receiving SC alone. At Day 10 (216 hours or Discharge), 13 of 14 (92.9%) patients receiving Auxora+SC (all doses) were able to tolerate solid food compared to 3 of 7 (43%) patients receiving SC alone. The median (min, max) time to tolerating solid food for patients receiving the low dose regimen+SC was 57 hours (17, 121), for patients receiving the high dose regimen, 78.5 hours (39, 440) and for patients receiving only SC, 100 hours (22, 720).

Five of 14 patients (35.7%) randomized to Auxora+SC (all doses) had persistent SIRS, defined as SIRS lasting continuously for \geq 48 hours starting on or after the Day 1 (0 hour) assessment, compared to 5 of 7 patients (71.4%) in the SC alone group.

A blinded central reader read all Screening, Day 5 or Discharge, and Unscheduled contrast-enhanced computed tomography (CECT) scans and gave a score for the severity of AP using the CTSI scoring system. One patient treated with the high dose regimen+SC did not receive a CTSI score at either the Screening or Day 5 or Discharge CECTs. One patient treated with SC alone did not receive a CTSI score at Screening because contrast was not given. On the Screening CECT, 8 patients treated with Auxora-IE+SC (all doses) had moderate or severe AP based on the CTSI score. Three of the 8 (37.5%) patients with moderate or severe AP improved with treatment to have mild AP based on the CTSI score on the Day 5 or Discharge CECT. On the Screening CECT, 4 patients treated with SC alone had moderate or severe AP. None of the 4 (0%) patients improved to have mild AP by the Day 5 or Discharge CECT.

The median length of stay (min, max) for patients randomized to Auxora-IE+SC (all doses) and SC alone were 3.70 (1.5, 18.3) and 6.02 (1.1, 30.0) days, respectively.

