8 VISITS AND ASSESSMENTS

8.1 Screening

The PI or designee must provide informed consent to the patient, or LAR, allowing the patient or LAR adequate time to consider, ask questions and receive answers, prior to agreeing to participate.

• Record the time of the patient or LAR provides informed consent

After informed consent is obtained, the following procedures are to be performed unless already performed as part of SOC:

- Record the time of the onset of abdominal pain that sent patient to ER
- Record demographics and medical history
- Record list of medications being taken prior to hospitalization
- Record vital signs closest to the time of informed consent
- Perform an abdominal examination specifically assessing for guarding and rebound tenderness (see Section 8.12.3)
- Draw serum pregnancy test if the patient is a female of childbearing potential analyze at local lab
 - If already performed as part of SOC, record results. Testing may be performed on blood drawn in the previous 12 hours prior to Consent or following consent but prior to randomization.
- Draw a blood sample for serum lipase–analyze at local lab
 - If already performed at local lab as part of SOC, record results. Testing may be performed on blood drawn in the previous 12 hours prior to Consent or following consent but prior to randomization.
- Draw a blood sample for CBC, differential, and platelets—analyze at local lab
 - If already performed at local lab as part of SOC, record results. Testing may be performed on blood drawn in the previous 12 hours prior to Consent or following consent but prior to randomization.
- Determine if SIRS is present (see Section 8.12.13)
- Obtain CECT of the abdomen/pancreas and determine if there is evidence of pleural
 effusion, peripancreatic fluid collection, pancreatic necrosis, pancreatic calcifications,
 pancreatic pseudocysts, and previous necrosectomy/previous pancreatic surgery are
 present on a CECT
 - o If CECT already performed in the 24 hours prior to the patient or LAR providing informed consent, use results from that CECT (see Section 8.12.12)

If the patient satisfies all of the inclusion criteria and none of the exclusion criteria, immediately proceed to Baseline Assessment.

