8.3 Randomization Using IXRS System

8.4 Start of First Infusion of Study Drug (SFISD)

The SFISD should begin within 8 hours of the patient or LAR providing informed consent.

Perform the following procedures immediately prior to the SFISD:

- Record concomitant medications
- Infuse the first dose of study drug
 - Record the time of the SFISD
 - o Record the time when the infusion is finished
 - Draw blood sample for PK as soon as possible after completion of the first infusion of study drug (within +2 hours)
- Begin Enhanced Recovery Strategy for Tolerance of Solid Food (see Section 5.2) and continue daily until patient discharge.

8.5 24 hours

24 hours from the SFISD:

- Record concomitant medications
- Record vital signs closest to the scheduled time of assessment
- Record the patient's pain using the PNRS closest to the scheduled time of assessment
- Record SpO₂ and the FiO₂ (see Section 8.12.6) closest to the scheduled time of assessment
- Determine if, and when the patient tolerated solid food in the previous 24 hours (see Section 5.2)
- Determine if the patient met the medically indicated discharge criteria in the previous 24 hours (see Section 5.3)
- Perform AE/SAE assessment
- Prior to the infusion of the second dose of study drug:
 - Draw blood samples for CBC, differential, platelets, Serum Procalcitonin and Serum Chemistries - analyze at local lab. Testing may be performed on blood drawn in the previous 12 hours.
 - Draw blood sample for Serum IL-6 send to central lab. Testing may be performed on blood drawn in the previous 12 hours.
 - O Draw blood sample for PK prior to the infusion of the second dose of study drug (within -30 min) send to central lab.
 - Obtain urine sample for Urine NGAL-send to central lab. Testing may be performed on urine collected in the previous 12 hours.
- Start the infusion of second dose of study drug 24 hours (±1 hour) from the SFISD (see Section 5.3)
 - o Record the time when the infusion starts and finishes

8.6 48 hours

48 hours from the SFISD:

- Record concomitant medications
- Record vital signs closest to the scheduled time of assessment
- Record the patient's pain using the PNRS closest to the scheduled time of assessment
- Record SpO₂ and the FiO₂ (see Section 8.12.6) closest to the scheduled time of assessment
- Determine if, and when the patient tolerated solid food in the previous 24 hours (see Section 5.2)

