- Determine if the patient met the medically indicated discharge criteria in the previous 24 hours (see Section 5.3)
- Perform AE/SAE assessment
- Prior to the infusion of the third dose of study drug:
 - Draw blood samples for CBC, differential, platelets, Serum Procalcitonin and Serum Chemistries – analyze at local lab. Testing may be performed on blood drawn in the previous 12 hours.
 - O Draw blood sample for Serum IL-6 send to central lab. Testing may be performed on blood drawn in the previous 12 hours.
 - Obtain urine sample for Urine NGAL send to central lab. Testing may be performed on urine collected in the previous 12 hours.
- Start the infusion of third dose of study drug 48 hours (±1 hours) from the SFISD (see Section 5.3)
 - o Record the time that the infusion starts and finishes
- Assess whether patient discharge is upcoming and whether mGCSI-DD worksheets need to be dispensed per Section 8.12.10.

8.7 72 hours

For patients who remain hospitalized 72 hours from the SFISD:

- Record concomitant medications
- Record weight closest to the scheduled time of assessment
- Record vital signs closest to the scheduled time of assessment
- Record the patient's pain using the PNRS closest to the scheduled time of assessment
- Record SpO₂ and the FiO₂ (see Section 8.12.6) closest to the scheduled time of assessment
- Determine if, and when the patient tolerated solid food in the previous 24 hours (see Section 5.2)
- Determine if the patient met the medically indicated discharge criteria in the previous 24 hours (see Section 5.3)
- Perform AE/SAE assessment
- Draw blood samples for CBC, differential, platelets, Serum Procalcitonin and Serum Chemistries analyze at local lab. Testing may be performed on blood drawn in the previous 12 hours or + 2 hours from assessment.
- Draw blood sample for Serum IL-6 send to central lab. Testing may be performed on blood drawn in the previous 12 hours or + 2 hours from assessment.
- Draw blood sample for PK \pm 2 hours send to central lab

- Obtain urine sample for Urine NGAL send to central lab. Testing may be performed on urine collected in the previous 12 hours or + 2 hours from assessment.
- Assess whether patient discharge is upcoming and whether mGCSI-DD worksheets need to be dispensed per Section 8.12.10.

8.8 96, 120, 144, 168, 192, 216, 240 hours (±4 hours)

For patients who remain hospitalized 96, 120, 144, 168, 192, 216, and 240 hours from the SFISD:

- Record concomitant medications

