- b. The most extreme value for each criterion in the 24 hours before consent or following consent but prior to randomization may be used.
- ^{c.} A CECT already performed in the 24 hours prior to the patient or LAR providing informed consent may be used as the Screening CECT. In addition to the Screening and the Day 30 visit CECTs, CECTs performed as standard of care after randomization and to 25 days after SFISD will be captured and submitted for central reading. If the CECT is performed 25 to 29 days after SFISD, it will substitute for the Day 30 visit CECT scan and will be captured.
- d. Hematocrit collected as standard of care within 12 hours of consent or following consent but prior to randomization may be used for Inclusion Criterion 3c.
- e. Biomarker blood and urine samples and blood samples for PK will be analyzed at central laboratory. If site or patient does not participate in these assessments this will be documented at start of study and will not be considered a protocol deviation.
- f. Determine if patient had met the medically indicated discharge criteria within the prior 24- or 48-hour visit assessment.
- Patients will be offered a low fat, ≥500-calorie solid meal at each mealtime after the infusion of the first dose of study drug until discharge if alert and not on mechanical ventilation, or if not NPO for a planned surgery/medical procedure, or if not NPO because of an acute medical condition. If the patient does not wish to eat the solid meal when offered or is unable to tolerate the solid meal, they should then be offered a liquid meal. Determine for each meal if the patient ate ≥50% of the meal without vomiting or having abdominal pain in the two hours after the meal.
- h. The mGCSI-DD score will be completed by all eligible patients at the baseline assessment and on the day of discharge, which will vary by patient as shown in schedule above. In addition, if the patient remains hospitalized at 96 and/or 168 hours and/or at Day 14 and/or Day 21 patient should be requested to record their symptoms at bedtime using the mGCSI-DD worksheet. Patients will be trained on completing the mGCSI-DD worksheet. Upon discharge, patient will record the mGCSI-DD score daily before bedtime until the Day 30 visit.

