8.7.7 Persistence of SIRS ≥48 Hours After the SFISD

The persistence of SIRS ≥48 Hours after the SFISD is defined by the presence of at least two of the following four criteria at the first visit 48 hours after the SFISD:

- Temperature $< 36^{\circ}$ C or $> 38^{\circ}$ C;
- Heart rate > 90 beats/minute;
- Respiratory rate >20 breaths/minute or arterial carbon dioxide tension (PaCO2) <32 mmHg;

Protocol CM4620-203 CONFIDENTIAL Page 21 of 31

• White blood cell count (WBC) >12,000 mm3, or <4,000 mm3;

The proportion and 95% CI of patients who developed persistence of SIRS ≥48 Hours After the SFISD will be displayed and analyzed in the same way as the re-hospitalization for acute pancreatitis through Day 30. If the patient is discharged before 48 Hours after the SFISD, the last available post-treatment data will be used to define the SIRS status at 48 hours after the SFISD based on the LOCF method.

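### SAP 8.7.7 labels SIRS at one 48-hour visit "persistence" without regard to SIRS status before dosing; this mislabels a secondary endpoint and costs some precision, but does not bias the arms

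*Protocol*

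**What the plan says.** **Entry.** SIRS is at least two of four criteria. Protocol 8.12.13 allows this: "The most extreme value for each criterion in the 24 hours before consent may be used". Appendix 8 footnote b is wider: "The most extreme value for each criterion in the 24 hours before consent or following consent but prior to randomization may be used". Neither asks that the qualifying values occur together.

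**Dosing.** Protocol 8.4: "The SFISD should begin within 8 hours of the patient or LAR providing informed consent". Appendix 8 schedules the SIRS determination at Screening only. The last scheduled vital signs before dosing are also at Screening, where Protocol 8.1 says: "Record vital signs closest to the time of informed consent". None are scheduled at Baseline or immediately before the first infusion.

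**Outcome.** SAP 8.7.7 defines persistence as the "presence of at least two of the following four criteria at the first visit 48 hours after the SFISD". The fourth criterion there omits the immature-forms limb used at entry. For a patient discharged before 48 h, "the last available post-treatment data will be used to define the SIRS status at 48 hours after the SFISD based on the LOCF method". For the 48 h blood count, Protocol 8.6 says: "Testing may be performed on blood drawn in the previous 12 hours".

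**Analysis.** SAP 8.7.7 refers to the re-hospitalization method in 8.7.4, a CMH test stratified by sex and organ-failure risk. Under SAP 8.1.3 the default denominator is the whole group. SAP 8.1.4.1 defines baseline as the last assessment up to the first infusion, but 8.7.7 does not use it. The SIRS subgroup in SAP 8.12 (two v more than two criteria) covers only time to solid food tolerance and the composite.

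**The concern.** The word persistence implies a condition that was present and did not go away. The rule counts something else: presence at one visit. Two kinds of patient are misdescribed.

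- A patient who qualified on scattered worst values and no longer had SIRS at the first dose is scored as not persistent, whichever arm they are in.
- A patient without SIRS at dosing who develops it by 48 h is scored as persistent.

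Patients with no SIRS at dosing have nothing to resolve. Pooled with the rest, they pull the arm rates together and add variation that a pre-dose covariate could explain. At stake are the meaning of one secondary endpoint and some of its precision. The primary gMCP-Mod analysis and the composite do not use it.

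**Working it through.** **1. The plan's own figure.** No power is stated for SIRS. The stated 80% (Protocol 10.2, SAP 4) is for solid food, 45% v 20%, 54 per arm, two-sided 0.05. With z = (|p1 − p2|√n − 1.96√(2p̄q̄)) / √(p1q1 + p2q2):

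(0.25 × 7.348 − 1.96 × 0.6624) / 0.6384 = 0.844, giving power 80.1%. It reproduces, but says nothing about SIRS.

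**2. Age of the values at dosing.** Qualifying value: 24 h + 8 h = about 32 h. Vital signs nearest consent: about 8 h. CBC: 12 + 8 = about 20 h under the 12 h window (Protocol 8.1; Appendix 8 footnote a), or 24 + 8 = about 32 h under the 24 h window (Protocol 8.12.7).

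**3. Dilution.** Let s be the share with SIRS at baseline, p the 48 h rate in those patients, and r the 48 h rate in the rest, equal in both arms. Arm rate = s·p + (1 − s)·r, so the difference shrinks to s × (p0 − p1). The documents give neither s nor r. Assumed: s = 50-80%, r = 10%. For p, two illustrative pairs: 71.4% v 35.7% (the 5/7 and 5/14 in Protocol 1.5.2) and 50% v 25% (assumed). With the first pair:

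- s = 80%: 59.1% v 30.6%, difference 28.6 points (from 35.7)
- s = 50%: 40.7% v 22.9%, difference 17.9 points

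**4. What a baseline-SIRS stratum buys.** Simulation, 54 v 54, 40,000 trials per setting, two-sided 0.05, sex and risk strata left out. Power, %:

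| s | 71 v 36: no stratum | with stratum | 50 v 25: no stratum | with stratum |
|---|---|---|---|---|
| 80% | 84 | 90 | 62 | 64 |
| 70% | 76 | 83 | 52 | 55 |
| 60% | 66 | 75 | 42 | 46 |
| 50% | 52 | 62 | 33 | 37 |

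The gain is 5-10 points at 71% v 36% and 2-4 points at 50% v 25%. With sex and risk strata included it was 4-9 and 2-3 points. Under the null, rejection stays at 4-5% in every setting.

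**5. Imperfect baseline status.** If recorded baseline SIRS has 80% sensitivity and 80% specificity (assumed), power with the stratum is 86/78/68/55% at 71% v 36%, a gain of 2-3 points. At 50% v 25% the gain is 0-1 point. Type I error is again near 5%.

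**6. Subset with baseline SIRS only.** At 71% v 36%, with status known exactly, power is 92/89/84/76%. With 80% accuracy it is 83/76/67/56%, about the same as the unstratified test in all patients. At 50% v 25% with 80% accuracy it is 56/50/42/35%, against 62/52/42/33% unstratified. The subset's advantage therefore depends on accurate baseline status.

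**The case against.** **No bias, and a minor endpoint.** Pre-dose recovery is balanced by randomization, and this is one of eleven listed secondary endpoints, with no power claim. Every patient met SIRS at entry, so presence at 48 h is a defensible loose reading of persistence. All of this stands. It limits the point to labelling and efficiency.

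**The size is unknown.** This stands. The 24 h rule is permissive, so not every patient enters on scattered values, and the share without SIRS at dosing is not given.

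**The 52-84% column is not the trial's power.** A reader might infer that it is. The documents do not support that. The 5/7 and 5/14 in Protocol 1.5.2 use the full arms of Table 3 as denominators, so they already contain any patient without SIRS at time 0; diluting them again counts the loss twice. As all-patient rates they give about 97% power at 54 per arm. An all-patient 71.4% with r = 10% would also need a rate of (0.714 − 0.04)/0.6 = 112% among baseline-SIRS patients at s = 60%, which is impossible; s must be at least 0.614/0.9 = 68%. The rates also come from 21 open-label patients under a different definition. They serve only to illustrate the gain from the stratum.

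**Phase 2a is not a precedent for requiring SIRS at dosing.** A reader might infer that it was. Its definition needed SIRS lasting continuously for at least 48 h "starting on or after the Day 1 (0 hour) assessment", which admits SIRS that began later. It differs from SAP 8.7.7 in requiring continuity, not in requiring SIRS at time 0.

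**The proxy is imperfect.** This also stands. Values nearest consent can predate dosing by hours. That is why the subset should not replace the all-patient test. A stratum fixed before dosing remains valid even when misclassified; it then gains less.

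**Conclusion.** The point holds as one of labelling and precision. SAP 8.7.7 measures presence of SIRS at one visit in all MITT patients and calls it persistence, although entry SIRS need not have been present at dosing. There is no bias between arms and no effect on the primary analysis.

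A baseline-SIRS stratum adds about 4-10 points of power at 71% v 36%, about 2-4 points at 50% v 25%, and about 0-3 points if baseline status is 80% sensitive and specific. Type I error stays near 5%, and power did not fall in any setting run. These figures rest on an assumed 50-80% with baseline SIRS and an assumed 10% with SIRS at 48 h among the rest. The documents support neither a specific power loss for this trial nor a claim that treated and placebo patients are compared unfairly.

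**What to change.** In SAP 8.7.7:

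1. Derive baseline SIRS (at least two criteria, as worded in 8.7.7 so that baseline and 48 h match) from the last recorded values before the first infusion under 8.1.4.1: the screening vital signs nearest consent and the last pre-dose CBC.
2. Add it as a stratum to the CMH test, keeping all MITT patients in the test.
3. Report the 48 h proportion among patients with baseline SIRS as a supportive persistence estimate, and describe the all-patient result as SIRS present at 48 h.
4. State that baseline SIRS is a proxy, with vital signs up to about 8 h old and the CBC up to about 20 or 32 h old at dosing, depending on the window.

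The cost is SAP wording and one derived variable from data already collected, with no new visits or patients.

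Separately, the passages that set the windows differ and must be reconciled. Before consent, the CBC window is 12 h in Protocol 8.1 and Appendix 8 footnote a, but 24 h for SIRS in Protocol 8.12.7. Protocol 8.12.13 does not mention the values between consent and randomization that footnote b allows.
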